2.1.2 Exploratory Objectives and Associated Endpoints

Table 3 Exploratory Objectives and Endpoints

Type	Objective	Endpoint
RSV neutralizing antibody	To determine anti-RSV neutralizing antibody levels in serum afforded by a single dose of MEDI8897 compared to 5 monthly doses of palivizumab	
 Anti-RSV neutralizing antibody levels (IU/mL) in serum for MEDI8897 recipients compared to palivizumab recipients Summary of serum RSV neutralizing antibody levels (may include GMT, GMFR, C_{max}, apparent clearance, and $t_{1/2}$)
RSV serology	To evaluate exposure to RSV by measuring seroresponses to different RSV proteins in MEDI8897 and palivizumab recipients	
 Antibody levels to RSV F, Ga, Gb, or N at different time points Changes in RSV antibody levels (seroresponse) indicating exposure to RSV
	To evaluate the levels of maternal RSV-specific antibody in MEDI8897 and palivizumab recipients	
 RSV antigen antibody levels (AbU/mL) to multiple RSV antigens Summary of serum RSV antibody levels (may include GMT, GMFR, seroconversion rates, apparent clearance, and $t_{1/2}$)
HRU and caregiver burden	To assess HRU and caregiver burden for MEDI8897 recipients compared to palivizumab recipients	
 Magnitude of HRU (eg, number of admissions to hospitals and ICUs and duration of stay; number of subjects who require respiratory support and supplemental oxygen and the duration of use; number and type of outpatient visits [eg, ER, urgent care, outpatient clinic]; and number of prescription and OTC medications and duration of use) for MEDI8897 recipients compared to palivizumab recipients Caregiver burden (eg, caregiver missed work days, subject absence from day care) for subjects with medically attended LRTI caused by RT-PCR-confirmed RSV

Table 3 Exploratory Objectives and Endpoints

Type	Objective	Endpoint
RSV resistance monitoring	To characterize resistance to MEDI8897 and palivizumab through genotypic and phenotypic analyses	Genotypic analysis and susceptibility of RSV variants to neutralization by MEDI8897 and palivizumab
RSV LRTI after Day 151	To assess the incidence of medically attended LRTI due to RT-PCR-confirmed RSV, compared to palivizumab after Day 151	Incidence of medically attended LRTI (inpatient and outpatient) due to RT-PCR-confirmed RSV from Day 152 to Day 361 for Season 1 and Season 2

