3.2.3 Rationale for Endpoints

MEDI8897 is being developed to provide RSV immunoprophylaxis for all infants entering their first RSV season and children with CLD of prematurity or hemodynamically significant CHD entering their first and second seasons. The primary endpoint for this study is safety and tolerability, with the aim of comparing the profiles for MEDI8897 and palivizumab in this population. The standard measures of TEAEs/TEAEs, AESIs, and NOCDs will be used for this assessment. All subjects will be followed for approximately 1 year after the last dose of MEDI8897. Subjects with CLD/CHD who receive MEDI8897 for Season 1 and Season 2 and subjects who receive a replacement dose of MEDI8897 after cardiopulmonary bypass will provide data for the safety assessment of infants who receive more than a single dose of MEDI8897.

Serum concentration of MEDI8897 at selected time points will be evaluated as a secondary endpoint to confirm that serum concentrations are maintained at an efficacious level for at least 5 months after dosing. Palivizumab serum concentrations will also be evaluated. MEDI8897 and palivizumab PK data will be summarized by non-compartmental analysis. Additionally, serum concentration data will be used to characterize the PK of MEDI8897 in infants using a population PK approach separately. For infants who require hospitalization for

LRTI or any respiratory infection, an additional serum sample for measurement of MEDI8897/palivizumab concentration and ADA will be obtained contemporaneous with time of hospitalization. Exposure-response analysis will be performed to relate MEDI8897 serum concentrations and efficacy endpoints (LRTI including RSV-associated hospitalization).

To determine MEDI8897 and palivizumab serum levels post dosing and to correlate with the potential development of ADA, serum concentrations will be measured up to 360 days post Dose 1 (when MEDI8897 would be given) for both Season 1 and, as applicable, Season 2. ADA to MEDI8897 and to palivizumab will be measured at selected time points throughout the study and up to 360 days post Dose 1 for each season as well.

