1 INTRODUCTION

This document describes the statistical analysis plan (SAP) for protocol D5290C00005, a pivotal Phase 2/3 randomized, double-blind, palivizumab-controlled study to evaluate the safety, PK, ADA response, and descriptive efficacy for MEDI8897 in high-risk infants eligible to receive palivizumab when entering their first or second RSV season (Season 1 or Season 2, respectively).

The primary objective of this study is to evaluate the safety and tolerability of MEDI8897 compared to palivizumab when administered to preterm infants entering their first RSV season and children with CLD or CHD entering their first and second RSV season. The secondary objectives are: (1) to evaluate serum concentrations of MEDI8897 and palivizumab, (2) to evaluate ADA responses to MEDI8897 and to palivizumab in serum, (3) to assess the descriptive efficacy of MEDI8897 when administered as a single IM dose of 50 mg to infants < 5 kg or 100 mg to infants ≥ 5 kg in the first RSV season or a single 200-mg IM dose administered in the second RSV season, in reducing medically attended LRTI (inpatient and outpatient) and hospitalization due to RT-PCR-confirmed RSV, compared to palivizumab

These objectives will be assessed by descriptive statistics from safety data, pharmacokinetic (PK) parameters, ADA, and the incidence of RSV LRTI and RSV hospitalization. This document details the statistical summaries relating to each study objective and describes the general conventions and definitions that will be used. Although formal hypothesis testing (for either safety or efficacy) will not be performed whereas only numerical summaries will be provided, an extrapolation study is planned to support extending the efficacy and safety data from the Phase 2b (D5290C00003) and Phase 3 (D5290C00004) studies in healthy preterm and term infants (ie, the palivizumab-ineligible population) to the target palivizumab-eligible population. The detail of the extrapolation will be provided in a separate PK extrapolation plan.

In addition, a set of templates and specifications for the tables, figures and listings is planned to be created in a statistical programming plan to complement this document.

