2.1.3 Exploratory Study Objectives

- 4 To assess HRU and caregiver burden for MEDI8897 recipients compared to palivizumab recipients
- To determine anti-RSV neutralizing antibody levels in serum afforded by a single dose of MEDI8897 compared to 5 monthly doses of palivizumab
- To evaluate exposure to RSV by measuring seroresponses to different RSV proteins in MEDI8897 and palivizumab recipients and to evaluate the levels of maternal RSV-specific antibody in MEDI8897 and palivizumab recipients

- 7 To characterize resistance to MEDI8897 through genotypic and phenotypic analyses
- 8 To assess the incidence of medically attended LRTI due to RT-PCR-confirmed RSV, compared to palivizumab after Day 151 (between Day 152 and Day 361)

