3 STATISTICAL METHODS

3.1 General Considerations

There are 3 planned analyses for this study: the primary analysis, the Season 2 analysis and the final analysis. The primary analysis will be conducted after all randomized subjects have completed follow-up through the first 5-month RSV season (ie, Season 1 Day 151 visit) and include all available Season 1 safety, efficacy, PK, and ADA data at the time of the data cutoff. The Season 2 analysis will be conducted after all CLD/CHD subjects have completed follow-up through the second 5-month RSV season (ie, Season 2 Day 151 visit) and include all available Season 1 data and Season 2 safety, efficacy, PK, and ADA data at the time of the data cutoff. The final analysis will be conducted when all subjects have completed the last visit of the study and include all data collected in the study.

At the time of the primary analysis, the Season 1 data will be unblinded to Sponsor/designated clinical research organization associated with the analysis, write-up and submission. To ensure the blinding of Season 2 treatment assignment for CHD/CLD subjects who were randomized to palivizumab arm in Season 1, any data with potential unblinding risk will be split by Season 1 and Season 2 by the corresponding third party data vendors and when the primary database lock (DBL) occurs, only unblinding data from Season 1 will be transferred to the Sponsor for analysis.

The site personnel, participants, and the study team members who participate in the advice or decisions involving study subjects and/or day-to-day interactions with the site, will remain blinded until the end of the study to ensure the trial integrity is maintained. Details of the unblinding process will be documented in a separated file of unblinding plan.

For the visit-based summaries for ADA, RSV neutralizing antibody, RSV serology, and clinical laboratory data, the summaries will be based on the scheduled days with adjusted analysis-defined visit windows. The adjusted analysis-defined windows will be based on the collection schedule listed in the protocol and summaries will be windowed to the closest scheduled visit for those data. Visit windows have been constructed so that every observation collected can be allocated to a particular visit. However, all data will be included in the listings. If multiple readings are recorded within a single analysis-defined visit window, the following rules will apply:

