3.6.3 Anti-RSV neutralizing antibody

For each season as well as the two consecutive seasons (ie, Season 1, Season 2, Season 1 + Season 2) the following summaries will be provided using the respective as-treated population. The Season 1 summaries will also be repeated for each cohort (pre-term, CHD/CLD).

Individual MEDI8897 and palivizumab serum RSV neutralizing antibody levels will be tabulated by treatment group along with descriptive statistics. RSV neutralizing antibody levels in serum will be summarized by geometric mean concentration and geometric meanfold rise and corresponding 95% CI for each treatment group at each visit. RSV neutralizing antibody level $t_{1/2}$ will be estimated using non-compartmental analysis, if data permit and may be reported outside the CSR.

Box plots of RSV neutralizing antibody levels in logarithm scale with base 10 will be provided by treatment group and by visit for each season.

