3.9 Pharmacokinetics

Individual MEDI8897 and palivizumab serum concentrations for each nominal sampling time will be listed and summary descriptive statistics presented by treatment group and cohort (preterm, CHD/CLD) in Season 1, and by treatment group in Season 2, respectively. Geometric mean MEDI8897 serum concentrations will be plotted versus time. Individual MEDI8897 serum concentrations will be graphically illustrated, and summarized, by ADA status.

Further, model-based evaluation of PK, and efficacy extrapolation, will be detailed in a separate PK extrapolation plan and reported outside the CSR.

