3.10 Impact on Analyses due to COVID-19 Pandemic

Scheduled visits, subject dosing, blood and nasal sample collection become difficult or impossible to perform according to protocol for subjects remaining in the study during COVID-19 pandemic.

Efforts are ongoing to collect outstanding data via alternative means where possible, when onsite visits cannot be performed. As a result, the following changes have been made to the planned analyses:

- Confirmed or suspected cases of COVID-19 will be listed as AEs and summarized as appropriate.
- An additional sensitivity analysis of medically attended RSV LRTI by Day 151 will be performed by excluding subjects who missed at least 1 active dose or had at least 1 active dose delayed for 7 or more days due to COVID-19 pandemic.
- COVID-19 related protocol deviations will be identifiable in the database with a 'COVID' prefix. COVID-19 related important protocol deviations will be summarized and described separately in the CSR.
- Subjects who miss a visit, miss blood or nasal sample collection, discontinue treatment or withdraw from study due to COVID-19 pandemic will be summarized.

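### Antibody and ADA visit windows set no maximum distance from the nominal day, and samples taken after a bypass replacement dose are pooled with single-dose samples

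*SAP*

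**What the plan says.** **Windows.** SAP 3.1 applies analysis windows to ADA, neutralizing antibody, serology and clinical laboratory data: "Visit windows have been constructed so that every observation collected can be allocated to a particular visit". In Appendix 2, the Global/Japan rows send Days 2-91 to Day 31 and Days 92-255 to Day 151. The EU rows have no Day 31 visit and send Days 2-255 to Day 151. Day 256 onward is Day 361 in both.

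**Choice within a window.** The sample nearest the scheduled day is used. For ADA, a positive overrides a negative in the same visit. For LRTI and unscheduled visits, SAP 3.1 gives only a rule for several samples on one day; it does not keep such samples out of the visit summaries.

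**Collection.** Protocol Table 5 schedules the Day 31 sample within 2 days either side and before dosing, and Day 151 within 7 days either side. Blood is also drawn at any respiratory hospitalization.

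**Purpose.** The exploratory objective in Protocol 2.1.2 concerns the neutralizing-antibody level "afforded by a single dose of MEDI8897 compared to 5 monthly doses of palivizumab", and SAP 2.1.3 repeats it. SAP 3.6.3 says that "RSV neutralizing antibody levels in serum will be summarized by geometric mean concentration", by group and visit. ADA incidence is a secondary endpoint (Protocol 2.1.1).

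**PK.** SAP 3.9 has "serum concentrations for each nominal sampling time will be listed and summary descriptive statistics presented by treatment group and cohort". PK is not in Appendix 2. Protocol 3.2.3 gives its aim as "to confirm that serum concentrations are maintained at an efficacious level for at least 5 months after dosing".

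**Extra doses.** SAP Table 1 cuts off PK and antibody data only after accidental receipt of both products. SAP 3.7.5 breaks safety results down by number of active doses. SAP 3.6.3, 3.6.4 and 3.9 have no such breakdown.

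**The concern.** If a scheduled sample is missing, a sample taken weeks or months away can be reported as the Day 31 or Day 151 value. The SAP gives reason to expect missing samples: Section 3.10 says "blood and nasal sample collection become difficult or impossible to perform according to protocol". The error need not cancel between arms. MEDI8897 decays from one dose, while palivizumab is re-dosed on Days 31, 61, 91 and 121, so the Day 31 window can hold palivizumab values taken after Dose 2 or later.

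Replacement doses raise a different problem. After bypass, even a punctual Day 151 sample reflects two MEDI8897 doses, so the nearest-sample rule gives no protection.

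Because "formal hypothesis testing (for either safety or efficacy) will not be performed", the descriptive tables are themselves the result, and the contrast they are meant to show is one MEDI8897 dose against monthly palivizumab.

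**Working it through.** **Inputs from the documents.** MEDI8897 half-life 56.5 days, range 46.8 to 81.1 (Protocol 1.4.1). Palivizumab half-life about 1 month (Protocol 1.1; 30 days used here). Palivizumab doses on Days 1, 31, 61, 91 and 121. MEDI8897 group of 600, of whom 200 in CLD/CHD.

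**Assumptions.** Mono-exponential decay; neutralizing antibody proportional to drug; absorption and maternal antibody ignored. The multiples below are for neutralizing antibody and drug level. They do not carry over to the serology antigens, which SAP 3.6.4 uses to follow maternal antibody and infection. The documents give no rate of missing samples or of bypass surgery.

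**1. Window widths (upper − lower + 1).**
- Global/Japan Day 31: 91 − 2 + 1 = 90 days
- Global/Japan Day 151: 255 − 92 + 1 = 164 days
- EU Day 151: 255 − 2 + 1 = 254 days
- Protocol collection windows, for comparison: 5 days (Day 31) and 15 days (Day 151)

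**2. One off-schedule MEDI8897 sample against its nominal day:** 2^((nominal day − sample day)/56.5).
- Day 31: sample on Day 2, 2^(29/56.5) = 1.43; on Day 91, 2^(−60/56.5) = 0.48
- Day 151: on Day 92, 2^(59/56.5) = 2.06; on Day 255, 2^(−104/56.5) = 0.28
- EU Day 151: on Day 2, 2^(149/56.5) = 6.2 (3.6 to 9.1 over the half-life range)
- At the edge of the protocol windows: 2^(2/56.5) = 1.025 and 2^(7/56.5) = 1.09

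**3. Palivizumab over the same windows:** sum of 2^(−(day − dose day)/30) over doses already given.
- Before Dose 2 on Day 31: 2^(−30/30) = 0.50
- Day 38: 2^(−37/30) + 2^(−7/30) = 1.28, or 2.6 times the Day 31 level. MEDI8897 on Day 38 is 2^(−7/56.5) = 0.92 times its own.
- Day 92 is 1.9 times the Day 151 level, and Day 255 is 0.09 times. MEDI8897 reads 2.06 and 0.28.

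Between-arm ratios can therefore move as well as each arm's level.

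**4. Effect on a geometric mean** when a share f of children has only an off-schedule sample: 2^(f × mean offset in days/56.5).
- EU Day 151, samples spread evenly over Days 2-151, mean offset 149/2 = 74.5 days: f = 5%, 1.047; f = 10%, 1.096; f = 20%, 1.20
- Global/Japan Day 151, f = 10%: early (mean 29.5 days) 1.037; late (mean 52 days) 0.938
- Global/Japan Day 31, f = 10%: early (mean 14.5 days) 1.018; late (mean 30 days) 0.964

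**5. Replacement dose.** A single dose leaves 2^(−150/56.5) = 0.159 on Day 151.
- Equal-size replacement on Day 85: 2^(−66/56.5) = 0.445. Ratio 0.445/0.159 = 2.8 if bypass removed all of the first dose, 3.8 if it removed none.
- Half-size replacement on Day 90: 0.5 × 2^(−61/56.5) = 0.237. Ratio 1.5 to 2.5.
- If 5-10% of the 200 CLD/CHD children on MEDI8897 are replaced (10 to 20 children) at 2.8-fold, the cohort geometric mean rises by 2.8^0.05 = 1.05 to 2.8^0.10 = 1.11. Over all 600 it rises by 2.8^(10/600) = 1.017 to 2.8^(20/600) = 1.035.

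**The case against.** The nearest-sample rule in SAP 3.1 is the strongest answer. Any child with a punctual neutralizing-antibody or serology sample contributes that sample, and a moderately late one still displaces a distant hospitalization sample. The window boundaries follow a stated logic: (31 + 151)/2 = 91 and (151 + 361)/2 = 256 are midpoints between visits, and the lower limit of Day 2 keeps the baseline separate. All data are listed, SAP 3.6.3 provides box plots by visit, and SAP 3.10 counts blood samples missed because of COVID-19. Neutralizing antibody is exploratory and nothing is tested. Replacement doses concern only CLD/CHD children with bypass between Dose 1 and Dose 5, and children with surgery anticipated within 2 weeks are excluded. All of this stands, and it limits the size.

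It does not remove the point. The nearest-sample rule sets no outer limit, does not govern ADA and does nothing about replacement doses. Listings let a reader find stand-in values but leave them in the geometric means.

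A reader might infer more than the documents support:
- *That the windows undermine the 5-month PK confirmation.* They do not cover PK, which is summarized by nominal time. Only the missing replacement-dose rule touches the descriptive PK table, and model-based PK is left to a separate plan.
- *That values are wrong by up to 2^(253/56.5) = 22-fold.* That compares the two edges of the EU window. The relevant error is against the nominal day, for one child.
- *That 254 days is the general width.* It is the EU Day 151 row only.
- *That the tables fail to show single-dose levels.* Without a rate of missing samples or replacements, this is not established.

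**Conclusion.** The point holds as a possible, mostly modest contamination of the visit summaries.

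- **Windows, neutralizing antibody.** Only children without a nearer sample matter. If 5-20% of EU children have only an off-schedule sample spread over Days 2-151, the EU Day 151 geometric mean rises about 5-20%. At 10%, the Global/Japan shifts run from about −6% to +4%.
- **Windows, ADA.** By-visit percentages are more exposed, since an early EU positive can count as Day 151. The table of any post-baseline positive (SAP 3.8) does not depend on the windows.
- **Replacement doses.** At 5-10% replaced and a 2.8-fold rise, the CLD/CHD geometric mean rises about 5-11% and the mean over all 600 about 1.7-3.5%. The preterm cohort is untouched.

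These sizes rest on assumed rates, simple exponential decay and the Phase 2b median half-life. No test or sample size depends on them. The change is worth making because it is cheap and brings the tables into line with the stated single-dose contrast.

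**What to change.** 1. In SAP 3.1 and Appendix 2, set a maximum distance from each nominal day and require Day 31 samples to precede Dose 2. At the least, add a supportive summary restricted to the protocol's collection windows (Day 31 ± 2 days, pre-dose; Day 151 ± 7 days). The exact limit is the sponsor's choice; what matters is that one is fixed before unblinding.
2. State that hospitalization and other unscheduled samples are listed and do not enter the visit geometric means.
3. In SAP 3.6.3 and the descriptive PK table of 3.9, show samples taken after a replacement dose in a separate row and leave them out of the single-dose summary.

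The cost is SAP wording, some programming and a few more missing values per visit. No data collection or dosing changes.
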